### 5.5 Risk/Benefit

In adult healthy volunteers and pediatric patients with cholestatic liver disease, odevixibat has been generally safe and well tolerated in all completed studies. Reported AEs have primarily been of mild intensity. Abdominal pain and diarrhea have been the most common AEs in adults, and only 1 AE of diarrhea was reported in the pediatric Phase 2 study. Based on the mode of action of odevixibat as an IBAT inhibitor, loose stools or diarrhea are expected.

Infants with ALGS have elevated serum bile acids. Serum bile acids are an indicator of elevated bile acids within the liver, which in turn are thought to play a contributory role in hepatic oxidative stress and fibrosis. It has been shown that serum bile acid levels can predict long-term outcomes in patients with biliary atresia; even in patients with successful Kasai HPE procedures (defined as serum total bilirubin levels <1.5 mg/dL at 6 months post Kasai HPE); elevated serum bile acids may persist and can predict continued loss of hepatic function [Harpavat 2018]. Likewise, data from the Natural Course and Prognosis of Progressive Familial Intrahepatic Cholestasis (PFIC) and Effect of Biliary Diversion (NAPPED) consortium have shown that serum bile acid levels can predict long-term outcomes in patients with PFIC Type 1 [Van Wessel 2019] and Type 2 [Van Wessel 2020]. These clinical

observations, along with preclinical data demonstrating the adverse impact of elevated bile acids on the liver, provide support for the hypothesis that lowering serum bile acids may be of benefit in the long-term outcome of patients with cholestatic liver diseases including ALGS. By reducing the bile acid load, odevixibat has the potential not only to reduce the pruritus associated with chronic cholestasis, but also to ameliorate or slow hepatic injury or fibrosis and improve the long-term hepatic outcomes in patients with ALGS. The risk/benefit profile of odevixibat in patients with ALGS is considered acceptable.

## **6 STUDY OBJECTIVES**

### **6.1 Primary Objective**

- To demonstrate the efficacy of repeated daily doses of 120 µg/kg/day odevixibat in relieving pruritus in patients with ALGS.

### **6.2 Secondary Objectives**

[figure not shown]
- To assess the impact of odevixibat on serum bile acid levels in patients with ALGS.
- To evaluate the safety and tolerability of odevixibat in patients with ALGS.

**7 INVESTIGATIONAL PLAN**

**7.1 Overall Study Design and Plan**

This is a Phase 3, double-blind, randomized, placebo-controlled study to investigate the efficacy and safety of 120 µg/kg/day odevixibat in patients with ALGS.

**Figure 1 Study Design**

Odevixibat = once daily treatment with 120 µg/kg/day odevixibat

**7.1.1 Schedule of Assessments**

The schedule of assessments is presented in [Table 1](#). For information on blood volumes, please see [Appendix 7](#).

**Table 1 Schedule of Assessments**

Study Activity a	Screening Period b		Random-ization	Phone Call	Week 4	Week 8	Week 12	Week 16	Week 20	24 weeks/End of Treatment (EOT) c	Safety Follow-up d
	-56 to -21	-49 to -14									
Study Days	Clinic Visit 1	Clinic Visit 2	1	14 ± 3	28 ± 3	56 ± 3	84 ± 3	112 ± 3	140 ± 3	168 ± 3	196 ± 7
Clinic Visits	Clinic Visit 1	Clinic Visit 2	Clinic Visit 3	n/a	Clinic Visit 4	Clinic Visit 5	Clinic Visit 6	Clinic Visit 7	Clinic Visit 8	Clinic Visit 9	Clinic Visit 10
Phone Call				X							
Informed consent e	X										
Inclusion/exclusion criteria	X	X	X								
Demographics	X										
Prior and Concomitant medications f	X	X	X	X	X	X	X	X	X	X	X
Medical and surgical history	X	X	X								
Clinical Genetic Testing	X										
Full physical examination g	X		X								
Skin examination and symptom based physical examination g		X		X	X	X	X	X	X	X	X
Vital signs h	X	X	X	X	X	X	X	X	X	X	X
eDiary: itching, scratching, and sleep scores i	X	X					X				
Clinical chemistry j	X	X	X	X	X	X	X	X	X	X	X

Odevixibat (A4250)  
Protocol A4250-012

Study Activity a	Screening Period b		Random-ization	Phone Call	Week 4	Week 8	Week 12	Week 16	Week 20	24 weeks/End of Treatment (EOT) c	Safety Follow-up d
	-56 to -21	-49 to -14									
Study Days	Clinic Visit 1	Clinic Visit 2	1	14 ± 3	28 ± 3	56 ± 3	84 ± 3	112 ± 3	140 ± 3	168 ± 3	196 ± 7
Clinic Visits	Clinic Visit 1	Clinic Visit 2	Clinic Visit 3	n/a	Clinic Visit 4	Clinic Visit 5	Clinic Visit 6	Clinic Visit 7	Clinic Visit 8	Clinic Visit 9	Clinic Visit 10
Phone Call				X							
Hematology d	X		X		X		X			X	X
Urinalysis d	X						X			X	X
Serum bile acids (fasting k )	X	X	X		X	X	X	X	X	X	X
INR	X		X		X	X	X	X	X	X	X
Autotaxin l			X				X			X	
p-C4 l			X				X			X	
AFP			X							X	
Vitamins A (fasting k ) & E	X		X				X			X	
25-hydroxy vitamin D	X		X				X			X	
Blood sample for odevixibat PK l					X				X	(EOT only)	
Liver ultrasound and elastography (where available)			X							X	
QoL questionnaire (PedsQL)			X				X			X	
Patient/Caregiver/Clinician Global Impression of Change					X		X			X	

Study Activity a	Screening Period b		Random-ization	Phone Call	Week 4	Week 8	Week 12	Week 16	Week 20	24 weeks/End of Treatment (EOT) c	Safety Follow-up d
	-56 to -21	-49 to -14									
Study Days	Clinic Visit 1	Clinic Visit 2	1	14 ± 3	28 ± 3	56 ± 3	84 ± 3	112 ± 3	140 ± 3	168 ± 3	196 ± 7
Clinic Visits			Clinic Visit 3	n/a	Clinic Visit 4	Clinic Visit 5	Clinic Visit 6	Clinic Visit 7	Clinic Visit 8	Clinic Visit 9	Clinic Visit 10
Phone Call				X							
Patient/Caregiver/ Clinician Global Impression of Symptoms			X		X		X			X	
Clinician assessment of xanthoma			X				X			X	
Pregnancy test m	X serum	X urine	X urine		X urine	X urine	X urine	X urine	X urine	X urine	X urine
Study drug dispensed n			X		X	X	X	X	X	X	
Adverse events o	All Adverse Events										
FSV Deficiency Questionnaire	X	X	X	X	X	X	X	X	X	X	X
Study drug compliance				X	X	X	X	X	X	X	X
eDiary compliance i		X	X	X	X	X	X	X	X	X	X
Exit Interview										X	

AFP: alpha-fetoprotein; eCRF: electronic case report form; eDiary: electronic diary; EOT: end of treatment; FSV: fat soluble vitamin; ICF: informed consent form; INR: international normalized ratio; p-C4: plasma 7α hydroxy 4-cholesten-3-one; PedsQL: Pediatric Quality of Life Inventory; PK: Pharmacokinetic; QoL: quality of life; SAE: serious adverse event.

a All assessments will be performed before dosing unless otherwise noted.

b The two screening visits must be separated by at least 7 days, and Screening Visit 2 must occur at least 14 days prior to Study Day 1.

c An EOT visit must be performed as soon as possible if study drug is prematurely discontinued. The EOT visit requires the same assessments as the Week 24 visit.

d The Safety Follow-up visit is required 28 days (±7) following the Week 24/EOT visit or the date of last dose for patients who prematurely discontinued study treatment. See Section 7.1.3 and Section 7.1.4 for when a Safety Follow-up visit is not required.

- e The ICF (and assent) must be signed before any study procedures are performed.
- f Past (within 28 days prior to Screening Visit 1) and current medication will be documented in the eCRF.
- g A full physical exam including skin exam will occur at Screening Visit 1 and Day 1. At all other clinic visits a skin exam and symptom-based physical exam will occur. Findings from the symptom-based physical exam will be documented as adverse events if appropriate.
- h Includes blood pressure, pulse, respiratory rate, temperature, height (or length depending on age), and body weight.
- i Includes training on use of the device at Screening Visit 1, retraining (if applicable) at Screening Visit 2, and review of patient daily entries during 14 days prior to Day 1 to determine eligibility. eDiary compliance will be reviewed at all visits and the Day 14 phone call.
- j See [Table 4](#) for detailed parameters.
- k Patients will fast (water intake only is permissible) for at least 4 hours prior to the collection of samples for serum bile acid and vitamin A. Exceptions can be made for infants, less than 12 months of age, if unable to fast for the full 4 hours.
- l Samples will not be collected for patients  $\leq 10$  kg. In the event of an SAE, samples are to be collected as close to the onset of the event as possible.
- m For females who have reached menarche. If a urine pregnancy test is positive, a serum pregnancy test is to be performed to confirm the pregnancy.
- n Study drug to be taken once daily from randomization (Study Day 1) through the Week 24/EOT visit as described in [Section 7.1](#) and [7.1.2.2](#).
- o Serious adverse events will be collected from the time of signing of the ICF through study completion. Non-serious adverse events will be collected from the first dose of study drug through study completion. See section 10.1.1 for additional information.

### **7.1.2 Study Procedures and Assessments**

When conditions make it challenging for a patient to attend a visit at the study center and where applicable country and local regulations and infrastructure allow, routine assessments may be performed outside of the study center (eg, the patient's home) by a trained healthcare professional at all timepoints following randomization (Day 1). These assessments can include the following: vital signs, height and weight, blood draws, urine collection, and urine pregnancy test. All laboratory samples should be sent to the central laboratory; an exception is for situations related to the COVID-19 pandemic if central laboratory assessments are not possible, then a local laboratory may be used. These local lab results must be sent to the site for review by the Investigator and entry into the clinical database as applicable. Collection of other visit requirements, eg concomitant medication and AE collection associated with visits outside of the clinic will be collected by qualified site staff through verbal contact with the patient.

For any study visit, the study physician (or delegate) must, at a minimum, verbally contact the patient within the expected window for each study visit to collect relevant safety information (including, but not limited to, AEs, concomitant medications, hospitalizations/procedures, and vital status). Any missed assessment due to a study visit being performed outside of the study center will be considered a protocol deviation.

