### **9.2.2 Serum Bile Acids**

Blood samples for analysis of fasting total serum bile acid will be drawn at all clinic visits. Patients will fast (water intake only is permissible) for at least 4 hours prior to the collection of samples for serum bile acid. Exceptions can be made for infants, <12 months of age, if unable to fast for the full 4 hours. Any visit at which a bile acid sample result is unreportable, an additional unscheduled visit for a repeat sample collection may be scheduled. All post baseline serum bile acid will be blinded. Samples will be processed and transported to a central laboratory per instructions in the laboratory manual.

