All samples will be processed and transported to a laboratory per instructions in the laboratory manual. For the purposes of study conduct, only laboratory tests done in the central laboratory may be used. Local laboratories may be used at the discretion of the local investigator for management of urgent medical issues. If a local laboratory test value is found to be abnormal and clinically significant, it will be verified by the central laboratory as soon as possible after the investigator becomes aware of the abnormal result. If it is not possible to send a timely specimen to the central laboratory (e.g. the patient was hospitalized elsewhere), the investigator may base the assessment of an AE on the local laboratory value.

The observed laboratory values will be recorded and assessed according to the investigator’s clinical judgment.

Additional safety blood samples may be needed due to follow up of an abnormal value or analysis failure. The blood samples collected for safety laboratory analysis will be destroyed after the analyses have been completed.

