5.2 Appendix 2 Derived Variables

The table below provides the list of derived variables for demographic and baseline characteristics, various duration derivations, drug compliance, baseline derivations and other important protocol derivations applicable for this study.

Table 9 – Derivation rules for the derived variable

Variables	Formula
Demographic and Baseline characteristics	
Age (in years)	For patients not from site CCI : Age is calculated based on date of birth and date of randomization. It will be derived by SAS YRDIF function: yrdif (Date of birth, Date of Randomization, "ACT/ACT") For patients from site CCI : Only year of birth was collected, and January 1 was imputed in the eDC system. For analysis purpose, age is calculated based on collected age months and age years on the CRF.
Derivation of Duration	
Study day at any visit	Date of interest – Date of first dose of study drug. One day is added if this difference is ≥ 0
Extent of Exposure	
Duration of treatment exposure (days)	Date of last study drug intake – Date of first study drug intake + 1
Average Daily dose (ug/kg/day)	Sum of (number of capsules taken per day * dose strength of the capsules per weight category * dose duration under this dose amount/weight) / (Date of last study drug intake – Date of first study drug intake + 1)
Overall Study Drug Compliance	
Compliance	$100 \times \text{sum of (number of capsules actually taken)} / \text{sum of (number of capsules planned to be taken per day * dose duration under this planned dose amount)}$
Last participant date	Last contact date or date of death which occurred first
Derivation for Efficacy Parameters	
Baseline (general)	The baseline value of a parameter is defined as the last assessment of that parameter prior to the first intake of study treatment, except as indicated below
Baseline for serum bile acid	The baseline will be calculated as the average of the last 2 values prior to the first dose (central laboratory results will be used over local laboratory results). If only one non-missing value is available, it will be used as baseline.
Average serum bile acid of Week 20 and Week 24	The average of values that identified from analysis window at Week 20 and Week 24.
Daily score for ObsRO scratching (or PRO itching) severity	The daily score is calculated by averaging the PM score and the next day AM score. The daily score is calculated if at least the PM score or the next day AM score is collected.

Variables	Formula

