5.3 Appendix 3 Data Handling Conventions

Analysis windows for time points

The following analysis windows will decide how the scheduled and/or unscheduled visits will be used in the by-visit analyses of efficacy and safety variables. A measurement (scheduled or unscheduled) will be used if it is available and measurement date is within the analysis window.

After applying these time windows, if multiple assessments are associated to the same time point, the closest from the targeted study day will be used. In case of ties between observations located on different sides of the target day, the earlier assessment will be used. For laboratory parameters, central laboratory results will be used over local laboratory results if both are in a same analysis window.

Table 10.1 - Analysis visit windows (general)

Timing of assessment	Visit Name to display for Analysis	Targeted study day	Analysis window in study days / date of assessment
Screening	Baseline		<= -1
Randomization day 1	Baseline		1 (pre-dose)
Week 4	Week 4	28	Post-baseline to 42
Week 8	Week 8	56	43 to 70
Week 12	Week 12	84	71 to 98
Week 16	Week 16	112	99 to 126
Week 20	Week 20	140	127 to 154
Week 24	Week 24	168	155 to EOS ^a / 155 to EOS-1 ^b
4 Weeks Post Last Dose of Study Drug	Follow-up		EOS ^b

EOS=date of EOS assessment

^a For patients who rollover to Study A4250-015.

^b For patients who not rollover to Study A4250-015.

Table 10.2 - Analysis visit windows (GIC/GIS, PedsQL, xanthoma and selected lab tests)

Timing of assessment	Visit Name to display for Analysis	Targeted study day	Analysis window in study days / date of assessment
Screening	Baseline		<= -1
Randomization day 1	Baseline		1 (pre-dose)
Week 4	Week 4	28	Post-baseline to 56
Week 12	Week 12	84	57 to 126
Week 24	Week 24	168	127 to EOS ^a / 127 to EOS-1 ^b
4 Weeks Post Last Dose of Study Drug	Follow-up		EOS ^b

Note Selected lab tests include hematology, urinalysis, autotaxin, p-C4, Vitamins A & E and 25-hydroxy vitamin D.

EOS=date of EOS assessment

^a For patients who rollover to Study A4250-015.

^b For patients who not rollover to Study A4250-015.

Table 10.3 - Analysis visit windows (abdominal ultrasound and elastography, AFP)

Timing of assessment	Visit Name to display for Analysis	Targeted study day	Analysis window in study days / date of assessment
Screening	Baseline		<= -1
Randomization day 1	Baseline		1 (pre-dose)
Week 24	Week 24	168	71 to EOS ^a / 71 to EOS-1 ^b
4 Weeks Post Last Dose of Study Drug	Follow-up		EOS ^b

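### Protocol 7.1.2 sends COVID-19 local laboratory results to the investigator without exempting serum bile acid, although Protocol 9.2.2 says all post-baseline bile acid is blinded

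*Protocol*

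**What the plan says.** Protocol 7.1.2 lets routine assessments, blood draws among them, take place away from the study center after randomization. Its default is that every laboratory sample goes to the central laboratory, with one departure: "an exception is for situations related to the COVID-19 pandemic if central laboratory assessments are not possible, then a local laboratory may be used". It continues: "These local lab results must be sent to the site for review by the Investigator and entry into the clinical database as applicable".

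Protocol 9.2.2 deals with bile acid specifically: "Blood samples for analysis of fasting total serum bile acid will be drawn at all clinic visits"; "All post baseline serum bile acid will be blinded"; and "Samples will be processed and transported to a central laboratory per instructions in the laboratory manual". It mentions neither the local route nor how a local result would be kept from the site.

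Protocol 10.2.1 gives a third rule, "For the purposes of study conduct, only laboratory tests done in the central laboratory may be used", and allows local laboratories for urgent medical issues.

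The SAP mentions local results in three relevant places:
- Appendix 2 (Table 9), for the bile acid baseline: "central laboratory results will be used over local laboratory results".
- Appendix 3, for all by-visit windows: "For laboratory parameters, central laboratory results will be used over local laboratory results if both are in a same analysis window".
- Section 4.8.2.1, which falls back on local data when central data are missing because of COVID-19 or for other reasons, for a list of safety variables that does not include bile acid.

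**The concern.** Lowering serum bile acid is the stated rationale for the drug (Protocol 5.3), and bile acid is the key secondary endpoint (Protocol 9.1.2). A post-baseline value therefore carries information about the arm, which is a good reason to blind it. Protocol 8.4.3 requires investigators to be unaware of treatment, yet 7.1.2 makes it mandatory to send local results to them.

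The investigator assesses adverse event severity and causality (Protocol 10.1.2.4 and 10.1.2.5) and has discretion over dose modification (8.3). Site clinicians rate CGIC, CGIS and xanthoma (9.2.5 and 9.2.6). A hint about the arm could colour any of these judgements.

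There is a secondary measurement question. If a local Week 20 or Week 24 value were the only one in its window, it would be set against a baseline that is normally central, so the change would mix two laboratories.

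**Working it through.** **1. The rules side by side, for a post-baseline bile acid sample that the central laboratory cannot analyse because of COVID-19.**

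- 7.1.2: the default covers all laboratory samples; local analysis is allowed; the result must go to the investigator. Bile acid is not exempted and no recipient outside the site is named.
- 9.2.2: the result is blinded and the sample goes to a central laboratory. No exception is stated.
- 10.2.1: only central tests serve study conduct. COVID-19 is not mentioned.

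None of the three refers to the others on this point. If a local post-baseline bile acid result exists, a site cannot send it to the investigator and also keep it blinded.

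**2. The plan's own figure.** Inputs from Protocol 11.1: 36 completers at 2:1 (24 and 12), difference 1.2, SD 1.0, 1-sided alpha 0.025. The noncentrality is 1.2 / sqrt(1/24 + 1/12) = 1.2 / 0.3536 = 3.39 on 34 degrees of freedom. Exact t-test power is 0.909, as stated. Nothing in this point changes the power or the sample size.

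**3. How much one value says about the arm.** The only figure in the plan for the bile acid effect is the standardized effect of 1.2 for the key secondary endpoint (Protocol 11.1), which is the change to the average of Weeks 20 and 24. Assume normal changes with equal variance. Let x be the reduction in SD units, with mean d on odevixibat and 0 on placebo.

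- Separation: AUC = Φ(d/√2) = Φ(1.2/1.414) = 0.80.
- Best guess with prior 2/3 for odevixibat: call the patient active if x > c, where c = d/2 − ln(2)/d = 0.600 − 0.578 = 0.022.
- Correct on odevixibat: Φ(1.2 − 0.022) = 0.880. Correct on placebo: Φ(0.022) = 0.509.
- Overall: (2/3)(0.880) + (1/3)(0.509) = 0.757.
- Guessing odevixibat for everyone: 2/3 = 0.667.

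The gain is 9 percentage points, and the best rule still labels about 49% of placebo patients as active. Over assumed effects of 0.83 to 1.5, AUC runs from 0.72 to 0.86 and accuracy from 70.9% to 79.6%.

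**4. A single visit.** If the mean difference and SD are the same at both visits and the two changes correlate at r, the single-visit effect is 1.2 × sqrt((1 + r)/2), which cannot exceed 1.2. With r = 0.5 (an assumption; the documents give none) it is 1.2 × 0.866 = 1.04. Then c = 0.520 − 0.667 = −0.147, and accuracy is (2/3)Φ(1.187) + (1/3)Φ(−0.147) = (2/3)(0.882) + (1/3)(0.441) = 0.735.

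**The case against.** The best reply is that 7.1.2 was never meant to reach bile acid. It speaks of routine assessments, and the protocol's table of routine laboratory parameters (Table 4) omits bile acid. Section 9.2.2 is the specific rule and names only the central laboratory, and 10.2.1 is central-only for study conduct. On that reading the specific rule qualifies the general one and nothing is disclosed. The laboratory manual or the Blinding and Unblinding Plan may say so.

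This reading is tenable, so a reader should not infer that a site following 7.1.2 necessarily breaks the blind. It is not written down, however. Blood draws are on the 7.1.2 list and the routing default covers all samples. The closing qualifier in 7.1.2 can be read as limiting database entry only.

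A reader might also infer that the SAP expects local post-baseline bile acid values. The support is thin. The Table 9 rule concerns baseline, which 9.2.2 does not blind. The Appendix 3 rule is a generic preference that does not name bile acid. The explicit COVID-19 fallback in 4.8.2.1 leaves bile acid out. The SAP would admit such a value if it existed; it does not show that one is foreseen.

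It is also fair to object that the route opens only when central assessment is impossible because of COVID-19, and the documents give no frequency.

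**Conclusion.** The point stands as an unresolved conflict between 7.1.2 and 9.2.2 for any local post-baseline bile acid result. It does not establish that unblinding has occurred or must occur.

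The size is modest. At the plan's own effect of 1.2 the best guess of the arm is right about 76% of the time, against 67% from allocation alone, and about 73.5% for a single visit if r = 0.5. These figures assume normal changes with equal variance. Differences between laboratories and the fluctuation in bile acid that SAP 4.6.2.3.1 expects could blur a local value further. The number of patients affected is unknown and may be zero.

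The direct risk is to CGIC, CGIS and xanthoma ratings, adverse event causality and severity, and dose-modification decisions. Two stronger conclusions are tempting and not supported:

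- *That the primary endpoint is biased.* The caregiver scores it in an eDiary, and 7.1.2 sends results to the investigator. The risk is indirect and needs the information to reach the caregiver.
- *That other markers (p-C4, autotaxin, FGF19, drug concentration) are exposed in the same way, including to the hepatic adjudication committee.* Protocol 9.2.4 says only that these samples go to a laboratory under the laboratory manual. No text specifically returns those results to the investigator or gives them to the committee.

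**What to change.** **Protocol 7.1.2.** Exempt post-baseline serum bile acid from the local route and from investigator review of local results. Store the sample and ship it to the central laboratory when possible. If a local result is unavoidable, send it only to a recipient outside the site and the blinded study team. Cross-refer to 9.2.2 and 10.2.1 so that the three sections agree. If the laboratory manual or the Blinding and Unblinding Plan already says this, a cross-reference is enough.

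**SAP.** Flag every patient whose local post-baseline bile acid value reached the site, and report the count by arm after unblinding. Repeat the key secondary MMRM of 4.6.2.1 without local post-baseline bile acid values, which also removes the mixing of laboratories.

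**Cost.** A clarification of a line or two, one flag and one more run of an existing model. The downside is an occasional delayed or missing bile acid value. The SAP indicates that enrollment is complete, so the protocol line can act only on visits still to come; the SAP steps remain possible before database lock.
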